9. APPENDICES

9.1. Detailed Statistical Methodology for the Pattern Mixture Model

Patients are classified into three distinct patterns for missing data at Month 12:

1. Placebo patients: missing data will be assumed to be MAR and imputed by using MI estimated from placebo patients
2. Patisiran patients who have either missing data related to COVID-19 or missing data with the last dose of study drug received within 60 days of the scheduled time point: missing data will be assumed to be MAR and imputed by using MI estimated from on treatment patisiran patients
3. Patisiran patients who have missing data unrelated to COVID-19 and the last dose of study drug was received more than 60 days prior to the scheduled time point: missing data will be assumed to be MNAR and imputed using the copy reference (CR) approach

As a first step, patients with missing data at Month 12 will be assigned to a missing data pattern based on the criteria above.

Next, missing data for patients in patterns 1 and 2 above will be imputed using MI. Since the pattern of missing data within patients may be non-monotone, multiple imputation will be conducted among patisiran and placebo patients separately using the Markov Chain Monte Carlo (MCMC) method. For each treatment arm, the imputation model will include baseline tafamidis use, type of amyloidosis, NYHA class, age at randomization, ATTR amyloidosis disease stage, baseline 6-MWT, and all calculated values of change from baseline in 6-MWT at pre-specified visits. Below is a sample SAS code for the multiple imputation:

```
proc mi data=DATAIN out=DATA_STEP1 seed=234 nimpute=100;
  by treatment;
  em maxiter=300 converge=1e-4 itprint outem=outem;
  var baseline_variables 6MWT_base 6MWT_chg_m6 6MWT_chg_m9 6MWT_chg_m12;
  mcmc chain=multiple initial=em;
run;
```

For patisiran patients, the input dataset DATAIN will include only data collected while on treatment. Any data collected from patisiran patients after treatment discontinuation will be excluded from the input dataset. The MI procedure generates imputed values for all missing values. For patients in pattern 3, imputed scores will be discarded and replaced by imputed values using the CR approach. The imputation model will include baseline tafamidis use, type of amyloidosis, NYHA class, age at randomization, ATTR amyloidosis disease stage, baseline 6-MWT, and all calculated values of change from baseline in 6-MWT at pre-specified visits.

```
proc mi data=DATA_STEP1_2 out=DATA_STEP2 nimpute=1 seed=xxx;
  by _imputation_;
  class treatment;
  fcs nbiter=30 reg (6MWT_chg_m12 = baseline_variables 6MWT_base
    6MWT_chg_m6 6MWT_chg_m9);
  mnar model (6MWT_chg_m12 / modelobs=(treatment='placebo'));
  var baseline_variables 6MWT_base 6MWT_chg_m6 6MWT_chg_m9 6MWT_chg_m12;
run;
```

9.2. Calculation of Stratified Win Ratio p-value and Confidence Interval

Dong et al (2018) note that the logarithm of the stratified win ratio is asymptotically normally distributed with mean $\nu_{\log(WR)}$ and variance $\sigma_{\log(WR)}^2$, with these terms defined in equations 7b and 8 in their paper, respectively. The point estimate of the mean, $\hat{\nu}_{\log(WR)}$, is the logarithm of the stratified win ratio statistic defined in Section 6.6.2.2. The variance estimate, $\hat{\sigma}_{\log(WR)}^2$, is calculated under the null hypothesis of the same treatment effect in the patisiran and placebo groups.

Then $\hat{z} = \frac{\hat{\nu}_{\log(WR)}}{\sqrt{\hat{\sigma}_{\log(WR)}^2}}$ is a standard normal deviate from which the p-value is readily obtained.

The 95% confidence interval for the logarithm of the stratified win ratio is constructed as

$$\hat{\nu}_{\log(WR)} \pm 1.96 * \sqrt{\hat{\sigma}_{\log(WR)}^2}$$

and the limits of this confidence interval will then be exponentiated to construct the 95% confidence interval for the stratified win ratio.

9.3. Questionnaire/Scoring

In questionnaires, if multiple responses are provided to a single-response question, the question is deemed as missing.

9.3.1. Kansas City Cardiomyopathy Questionnaire (KCCQ)

The Kansas City Cardiomyopathy Questionnaire is a 23-item self-administered questionnaire developed to independently measure the patient's perception of their health status, which includes heart failure symptoms, impact on physical and social function, and how their heart failure impacts their quality of life within a 2-week recall period.

There are 10 summary scores for the KCCQ tool, which are calculated as follows:

1. Physical Function

Code responses to each of Questions 1a-1f as follows:

- Extremely limited = 1
- Quite a bit limited = 2
- Moderately limited = 3
- Slightly limited = 4
- Not at all limited = 5
- Limited for other reasons or did not do the activity = <missing value>

If at least 3 of Questions 1a-1f are not missing, then compute

- Physical function score = [(mean of the non-missing Questions 1a-1f) – 1]/4 * 100

2. Symptom Stability

Code the response to Question 2 as follows:

- Much worse = 1
- Slightly worse = 2
- Not changed = 3
- Slightly better = 4
- Much better = 5
- I've had no symptoms over the last 2 weeks = 3

The symptom stability score = $[(\text{Question 2}) - 1]/4 * 100$.

3. Symptom Frequency

Code responses to Questions 3, 5, 7 and 9 as follows:

- Questions 3 and 9
 - Every morning/night = 1
 - 3 or more times a week but not every day = 2
 - 1-2 times a week = 3
 - Less than once a week = 4
 - Never over the past 2 weeks = 5
- Questions 5 and 7
 - All of the time = 1
 - Several times a day = 2
 - At least once a day = 3
 - 3 or more times a week but not every day = 4
 - 1-2 times a week = 5
 - Less than once a week = 6
 - Never over the past 2 weeks = 7

If at least two of Questions 3, 5, 7 and 9 are not missing, then compute

- $S3 = [(\text{Question 3}) - 1]/4$
- $S5 = [(\text{Question 5}) - 1]/6$
- $S7 = [(\text{Question 7}) - 1]/6$
- $S9 = [(\text{Question 9}) - 1]/4$

The symptom frequency score = $(\text{mean of } S3, S5, S7, S9) * 100$.

4. Symptom Burden

Code responses to Questions 4, 6 and 8 as follows:

- Extremely bothersome = 1
- Quite a bit bothersome = 2
- Moderately bothersome = 3
- Slightly bothersome = 4
- Not at all bothersome = 5
- I've had no swelling/fatigue/shortness of breath = 5

If at least one of Questions 4, 6 and 8 is not missing, then compute

- Symptom burden score = $[(\text{mean of the non-missing Questions 4, 6 and 8}) - 1] / 4 * 100$

5. Total Symptom Score

Total symptom score = mean of the following available summary scores

- Symptom Frequency Score
- Symptom Burden Score

6. Self-efficacy

Code responses to Questions 10 and 11 as follows:

- Question 10
 - Not at all sure = 1
 - Not very sure = 2
 - Somewhat sure = 3
 - Mostly sure = 4
 - Completely sure = 5
- Question 11
 - Do not understand at all = 1
 - Do not understand very well = 2
 - Somewhat understand = 3
 - Mostly understand = 4
 - Completely understand = 5

If at least one of Questions 10 and 11 is not missing, then compute

- Self-efficacy score = $[(\text{mean of the non-missing Questions 10 and 11}) - 1] / 4 * 100$

7. Quality of Life

Code responses to Questions 12, 13 and 14 as follows:

- Question 12
 - It has extremely limited my enjoyment of life = 1
 - It has limited my enjoyment of life quite a bit = 2
 - It has moderately limited my enjoyment of life = 3
 - It has slightly limited my enjoyment of life = 4
 - It has not limited my enjoyment of life at all = 5
- Question 13
 - Not at all satisfied = 1
 - Mostly dissatisfied = 2
 - Somewhat satisfied = 3
 - Mostly satisfied = 4
 - Completely satisfied = 5
- Question 14
 - I felt that way all of the time = 1
 - I felt that way most of the time = 2
 - I occasionally felt that way = 3
 - I rarely felt that way = 4
 - I never felt that way = 5

If at least one of Questions 12, 13 and 14 is not missing, then compute

- Quality of life score = $[(\text{mean of the non-missing Questions 12, 13 and 14}) - 1] / 4 * 100$

8. Social Limitation

Code responses to each of Questions 15a-15d as follows:

- Severely limited = 1
- Limited quite a bit = 2
- Moderately limited = 3
- Slightly limited = 4
- Did not limit at all = 5
- Does not apply or did not do for other reasons = <missing value>

If at least 2 of Questions 15a-15d are not missing, then compute

- Social limitation score = $[(\text{mean of the non-missing Questions 15a-15d}) - 1] / 4 * 100$

9. Overall Summary Score

Overall summary score = mean of the following available summary scores

- Physical Limitation Score
- Total Symptom Score
- Quality of Life Score
- Social Limitation Score

10. Clinical Summary Score

Clinical summary score = mean of the following available summary scores

- Physical Limitation Score
- Total Symptom Score

9.3.2. Norfolk Quality of Life-Diabetic Neuropathy (QOL-DN)

Norfolk QOL-DN is a tool for assessing patients' perception of the effects of diabetes and diabetic neuropathy. There are 35 questions divided into 5 domains. The range of possible total scores is -4 to 136.

Part I: Symptoms

Items 1-7 (Part I) are a simple inventory of symptoms of neuropathy. The presence of the symptom is checked in whichever box applies, and an absence of a symptom is checked under "none." Positive responses are scored as 1; and negative responses, as 0.

Part II: Activities of Daily Life

Items 8-35 (Part II) pertain to Activities of Daily Life, and most of these are scaled on a 5-point Likert scale ranging from 0 ("Not a problem") to 4 ("Severe problem"). However, Questions 31 and 32 are scored differently. In Question 31, "Good", the middle item, is scored as 0. "Very Good" is scored as -1, "Excellent" is scored as -2. "Fair" is scored as 1, and "Poor" is scored as 2. In Question 32, "About the Same," the middle item, is scored as 0. "Somewhat better" is scored as -1, "Much better" is scored as -2. "Somewhat worse" is scored as 1, and "Much worse" is scored as 2.

Subscales and Scoring Algorithm

The Total QOL and 5 domains should be summed as follows:

- Total QOL (35 items) $\Sigma(1-7, 8-35)$
- Physical Functioning/Large Fiber (15 items) $\Sigma(8, 11, 13-15, 24, 27-35)$
- Activities of Daily Living (ADLs) (5 items) $\Sigma(12, 22, 23, 25, 26)$
- Symptoms (8 items) $\Sigma(1-7, 9)$
- Small Fiber (4 items) $\Sigma(10, 16, 17, 18)$
- Autonomic (3 items) $\Sigma(19, 20, 21)$

Domain scores are calculated as the rounded integer value of the average scores of non-missing included items multiplied by the number of items if at least 50% of the items are non-missing. A domain score is missing if more than 50% of the included items are missing.

If the scores for all 5 domains are non-missing, then Total QOL is the sum of scores of the 5 domains; however, if at least 1 of the domains is missing and at least 50% of the items (18 items) are non-missing, then Total QOL is calculated as 35 times the mean of the non-missing items, rounded to the nearest integer. Otherwise, Total QOL is deemed as missing.

Signature Page for VV-CLIN-004130 v1.0
ALN-TTR02-011 Statistical Analysis Plan

Approval	 T+0000
----------	--

Approval	 46:22 GMT+0000
----------	--

Signature Page for VV-CLIN-004130 v1.0
ALN-TTR02-011 Statistical Analysis Plan

IMAGING STATISTICAL ANALYSIS PLAN ALN-TTR02-011

1. INTRODUCTION

The APOLLO-B study (ALN-TTR02-011) is a Phase 3, randomized, double-blind, placebo-controlled, multicenter study designed to evaluate the efficacy and safety of patisiran in adult patients with ATTR amyloidosis with cardiomyopathy. The cardiac magnetic resonance (CMR) and technetium scintigraphy imaging assessments will be used to evaluate imaging manifestations of cardiac amyloid involvement and are planned to be conducted for subsets of patients who opt-in to having assessments performed by one or both imaging modalities during the APOLLO-B study.

CMR imaging and technetium scintigraphy are non-invasive methods of characterizing transthyretin amyloid burden in the myocardium. Their utility in the diagnosis and prognosis of ATTR amyloidosis with cardiomyopathy are well established.[Fontana 2015; Gillmore 2016; Martinez-Naharro 2019] With CMR, the extent of late gadolinium enhancement (LGE), elevation in native T1, and extracellular volume (ECV) correlate with amyloid burden and death.[Fontana 2014; Fontana 2015; Martinez-Naharro 2019] The utility of these imaging methods to assess response to disease-modifying therapies are presently unknown. Anecdotal reports suggest that certain therapies may be associated with regression of cardiac amyloid, as assessed by CMR or technetium scintigraphy.[Florian 2020; Groothof 2020] Neither imaging modality, however, has been prospectively evaluated in a blinded, placebo-controlled trial for ATTR amyloidosis. The exploratory analyses here may hence serve to identify mechanisms and markers of treatment response or disease progression.

This imaging statistical analysis plan (SAP) details comprehensive specifications of the CMR and technetium scintigraphy data summaries and statistical analyses in support of the clinical study report for Study ALN-TTR02-011.

Table, figure, and listing specifications for this analysis are contained in a separate document.

2. STUDY OVERVIEW

Cardiac magnetic resonance will be assessed in a subset of up to 60 patients and technetium scintigraphy will be assessed in a subset of up to 100 patients; CMR and technetium scintigraphy will be performed at select sites as optional imaging assessments to assess cardiac amyloid involvement. The assessments will be performed at baseline, Month 12, Month 18, Month 24, Month 36, and Month 48 as specified in the Schedule of Assessments in the study protocol (Table 1, Table 2, Table 3, and Table 4).

3. OBJECTIVES AND ENDPOINTS

Objectives	Endpoints
To evaluate the efficacy of patisiran compared with placebo treatment on manifestations of cardiac amyloid involvement	
Change from baseline at Month 12 in global average extracellular volume (ECV) (%) by CMRChange from baseline at Month 12 in normalized left ventricle (LV) total uptake by technetium scintigraphy

4. PATIENT POPULATION

The populations (analysis sets) are defined as follows:

- **CMR Analysis Set:** All patients who were randomized and received any amount of study drug and have at least one CMR assessment at baseline or post-baseline. Patients will be analyzed according to the treatment to which they were randomized.
- **Technetium Analysis Set:** All patients who were randomized and received any amount of study drug and have at least one technetium scintigraphy assessment at baseline or post-baseline. Patients will be analyzed according to the treatment to which they were randomized.
- **CMR All Patisiran Treated Analysis Set:** All patients who were randomized and received any amount of patisiran and have at least one CMR assessment at baseline or post-baseline. Patients receiving at least one dose of patisiran includes patients who received patisiran during the 12-month double blind (12m-DB) period and patients who first received placebo during the 12m-DB period and switched to patisiran during the open label extension (OLE) period.
- **Technetium All Patisiran Treated Analysis Set:** All patients who were randomized and received any amount of patisiran and have at least one technetium scintigraphy assessment at baseline or post-baseline. Patients receiving at least one dose of patisiran includes patients who received patisiran during the 12m-DB period and patients who first received placebo during the 12m-DB period and switched to patisiran during the OLE period.

The CMR Analysis Set and Technetium Analysis Set will be used to analyze the CMR and technetium scintigraphy endpoints, respectively, during the 12m-DB period. The CMR All Patisiran Treated Analysis Set and Technetium All Patisiran Treated Analysis Set will be used to summarize long-term CMR and technetium scintigraphy data, respectively, during patisiran treatment (see Section 5.5 for details).

5. GENERAL STATISTICAL METHODS

Details of general considerations, computing environment, baseline definitions, randomization stratification factors, multiple comparisons/multiplicity, analysis cutoff and database lock are specified in the APOLLO-B SAP (Section 5).

5.1. Determination of Sample Size

CMR and technetium scintigraphy assessments are planned to be conducted in approximately 60 patients and up to 100 patients, respectively.

For the change from baseline at Month 12 in global average ECV (%), assuming a mean treatment difference of -4.8 between patisiran and placebo in the treatment-naïve group and -3.0 in patients with baseline tafamidis, the weighted average treatment difference between patisiran and placebo in the overall population is approximately -4.3 (standard deviation = 4.6), assuming 70% are in the treatment-naïve group and 30% are in the baseline tafamidis group. A sample

size of 60 patients provides >90% power for a 2-sided test to detect a mean difference between treatment arms at a 2-sided alpha = 0.05.

For the change from baseline at Month 12 in normalized LV total uptake, assuming a mean treatment difference of -15.0 between patisiran and placebo in the treatment-naïve group and -9.4 in patients with baseline tafamidis, the weighted average treatment difference between patisiran and placebo in the overall population is approximately -13.3 (standard deviation = 14.0), assuming 70% are in the treatment-naïve group and 30% are in the baseline tafamidis group. A sample size of 100 patients provides >90% power for a 2-sided test to detect a mean difference between treatment arms at a 2-sided alpha = 0.05.

5.2. Baseline Definitions

For CMR and technetium scintigraphy parameters, baseline will be defined as the last non-missing value up to 6 weeks after the first dose of study drug.

For the CMR All Patisiran Treated Set and the Technetium All Patisiran Treated Set, baseline for patients who switched from placebo to patisiran will be redefined as the last non-missing value available on or after Month 9 in the 12m-DB period and prior to the first dose in the OLE period, unless otherwise specified. If a patient does not have a Month 12 assessment prior to the first dose in the OLE period, the redefined baseline will be defined as the last non-missing value available on or after Month 9 in the 12m-DB period and up to 6 weeks after the first dose in the OLE period.

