5.4. Baseline Definitions

For 6-MWT, baseline will be defined as the last non-missing value available prior to the first dose of study drug.

For other efficacy parameters, baseline will be defined as the last non-missing value available on or before the date of first dose of study drug, unless otherwise specified.

For TTR, baseline will be defined as the average of all records collected on study, including those from any unscheduled visits, prior to the date and time of first dose.

For each parameter of the 12-lead electrocardiogram (ECG), baseline will be defined as the average of all available readings from the last visit prior to the first dose of study drug.

For all other parameters, baseline will be defined as the last non-missing value available prior to the first dose of study drug, unless otherwise specified.

For the All Patisiran Treated Set, baseline for patients who switched from placebo to patisiran will be redefined as:

- For TTR, the redefined baseline will be calculated as the mean of all TTR assessments performed on or after Month 9 in the 12m-DB period and prior to the first dose in the OLE period.
- For all the other endpoints, the redefined baseline will be defined as the last non-missing value available on or after Month 9 in the 12m-DB period and prior to the first dose in the OLE period, unless otherwise specified. For longitudinal efficacy endpoints, if a patient does not have a Month 12 assessment prior to the first dose in the OLE period, the redefined baseline will be defined as the last non-missing value available on or after Month 9 in the 12m-DB period and up to 3 weeks after the first dose in the OLE period, unless otherwise specified.

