6.4. Efficacy Analyses

6.4.1. Global Average Extracellular Volume

The primary CMR endpoint is the change from baseline to Month 12 in global average ECV.

The primary analysis will be performed using an analysis of covariance (ANCOVA) model for the CMR Analysis Set. All available data will be included in the primary analysis. The outcome variable is the change from baseline in global average ECV, and the model includes baseline global average ECV as a continuous covariate and treatment arm as a fixed term. If the number of patients in either treatment arm is less than 15, descriptive statistics may be presented.

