7. CHANGES TO PLANNED ANALYSES

The SAP Amendment 1 includes more details previously not discussed in the original SAP. The details of the changes and rationales are listed in the table below.

Summary of Changes	Detailed Description/Rationale
Updated planned timepoints for CMR and technetium scintigraphy assessments	To align with protocol Amendment 3
Updated primary endpoint for technetium scintigraphy	Technetium uptake in the LV will be quantified as a unitless ratio of the activity in the LV wall to the activity of the injected dose. The normalized LV tracer uptake is a reasonable metric to assess changes in the same patient over time and may be more sensitive than the heart/lung ratio or visual scores.
Added baseline definition for imaging parameters as the last non-missing value up to 6 weeks after the first dose of study drug	To allow assessments collected shortly after start of study drug to be summarized with baseline assessment in order to reduce the amount of missing data. Imaging parameters are not expected to be meaningfully impacted within a short time after starting study drug.
Updated windowing rule for patisiran patients for Month 12 to include assessments taken up to 6 weeks after the first dose of patisiran in the OLE period	To allow assessments collected shortly after first OLE dose for patisiran patients to be summarized with Month 12 assessments in order to reduce the amount of missing data. Imaging parameters are not expected to be meaningfully impacted within a short time after the first dose in the OLE period.
Updated data handling to not treat data after tafamidis drop-in as missing	To align with handling of the tafamidis drop-in intercurrent event in the primary analysis of efficacy parameters in the main APOLLO-B SAP

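### The imaging baseline rule lacks a fallback condition, so where a patient has both scans an on-treatment scan replaces a valid pre-dose one

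*SAP*

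**What the plan says.** Imaging SAP Amendment 1, Section 5.2, sets one rule for all CMR and scintigraphy parameters: "baseline will be defined as the last non-missing value up to 6 weeks after the first dose of study drug". Nothing makes use of a post-dose scan depend on the absence of a pre-dose one.

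Section 7 of the same document gives two reasons for the window. The first is its purpose: "To allow assessments collected shortly after start of study drug to be summarized with baseline assessment in order to reduce the amount of missing data". The second is an assumption: "Imaging parameters are not expected to be meaningfully impacted within a short time after starting study drug". No figure or source supports the assumption.

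The second paragraph of Section 5.2 redefines baseline for placebo patients who switch to patisiran. There the post-dose window opens only under a condition: "If a patient does not have a Month 12 assessment prior to the first dose in the OLE period".

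Section 6.4.1 uses baseline twice in the primary CMR analysis. The outcome is change from baseline, and "the model includes baseline global average ECV as a continuous covariate and treatment arm as a fixed term". Section 6.4.2 uses a similar model for normalized LV total uptake.

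Section 5.3 schedules one baseline scan and then Month 12 in the double-blind period.

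**The concern.** A rule meant to fill gaps should act only where there is a gap. As written, a programmer must take the later of two evaluable scans, so a Week 5 scan displaces a valid pre-dose scan. That fills no gap and swaps a pre-randomised-treatment measurement for an on-treatment one.

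Two things follow for such a patient. Whatever drug effect is present at the post-dose scan drops out of the patisiran change score, with nothing corresponding in the placebo arm, so the estimated difference moves toward zero. The ANCOVA also adjusts for a value that treatment may already have altered. The Imaging SAP plans no sensitivity analysis restricted to pre-dose baselines.

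**Working it through.** **Inputs from the documents.** Imaging SAP 5.1: ECV effect -4.3, SD 4.6, 60 patients; normalized LV total uptake effect -13.3, SD 14.0, 100 patients; power above 90% for each, two-sided alpha 0.05. Main SAP 2.2: 1:1 allocation. Main SAP 6.6.1.1: dosing every 3 weeks, so 6 weeks covers two infusions, or three if the scan follows the Week 6 infusion.

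**Reproducing the plan's figures** (normal approximation, 30 and 50 per arm, assuming an even split within each imaging subset):

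- Weighted effects: 0.7 × 4.8 + 0.3 × 3.0 = 4.26 (stated as 4.3); 0.7 × 15.0 + 0.3 × 9.4 = 13.32 (stated as 13.3).
- ECV: standard error 4.6 × √(2/30) = 1.188; 4.3/1.188 - 1.96 = 1.66; power 95.2% (94.5% with the noncentral t).
- LV uptake: standard error 14.0 × √(2/50) = 2.8; 13.3/2.8 - 1.96 = 2.79; power 99.7%.

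Both agree with the plan.

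**Effect of an on-treatment baseline.** Let f be the share of patisiran patients whose baseline is an on-treatment scan, and g the share of the Month 12 effect already present at that scan. For the unadjusted change score,

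expected difference = planned difference × (1 - f × g).

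Under ANCOVA the loss f × g is multiplied by the slope of follow-up on baseline, so it is smaller when that slope is below 1. The documents give neither f nor g; both are assumptions. Linear accrual over the year gives g = 6/52 = 11.5% for a scan exactly at Week 6.

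| g | f | ECV difference (power) | LV uptake difference (power) |
|---|---|---|---|
| 0 (sponsor's assumption) | any | -4.30 (95.2%) | -13.30 (99.7%) |
| 11.5% (linear) | 10% | -4.25 (94.7%) | -13.15 (99.7%) |
| 11.5% | 25% | -4.18 (94.0%) | -12.92 (99.6%) |
| 11.5% | 100% | -3.80 (89.3%) | -11.77 (98.8%) |
| 25% (faster than linear) | 10% | -4.19 (94.2%) | -12.97 (99.6%) |
| 25% | 100% | -3.22 (77.5%) | -9.98 (94.5%) |

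Under linear accrual the largest loss is 0.115 × 4.3 = 0.50 ECV points, or 0.115 × 13.3 = 1.5 units of uptake, with f = 100%. With f = 10% it is 0.1 × 11.5% = 1.15% of the effect, or 0.05 ECV points.

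**What f covers.** It includes patients whose only baseline scan is post-dose as well as those with both scans. Only the second group is created by the missing condition.

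**The open-label baseline.** Its condition concerns a missing Month 12 scan, not the absence of any pre-dose scan. Once the condition is met, the rule again takes the last value, from Month 9 up to 6 weeks after the first open-label dose. An unscheduled pre-dose scan from Month 9 onward can therefore also be displaced. This reads the condition as referring to the scheduled Month 12 scan; if scans windowed to Month 12 under Section 5.3 count, that route largely closes, but Section 5.2 does not say which is meant.

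**The case against.** The strongest reply is that the situation is hardly ever going to arise. With one scheduled baseline scan, the last value is simply that scan, whichever side of the first dose it falls, and the rule already behaves as a fallback. If a first scan is unreadable and repeated, the first value is missing and the repeat is the only candidate. A true override needs two evaluable scans by Week 6. This stands, and it limits the size of the problem, but the wording still selects the wrong scan when the case occurs.

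The sponsor also discloses the window and states that no meaningful early change is expected. If so, nothing is lost. That assumption can justify using a post-dose scan when there is no other; it gives no reason to prefer one over a pre-dose scan.

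A reader might infer three stronger points, none of which the documents support:

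- *That part of the drug effect is in fact being subtracted from itself.* This needs both an early effect and a material number of two-scan patients, and the documents show neither.
- *That the omission is confined to the randomised comparison.* The open-label rule has a condition, but it too can displace a valid pre-dose scan.
- *That the rule contradicts the main SAP.* Section 5.4 there does end other efficacy baselines with "the last non-missing value available on or before the date of first dose of study drug", but it allows exceptions specified elsewhere, and the Imaging SAP specifies one and logs it.

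**Conclusion.** The wording defect is established: the rule lacks the condition that its stated purpose requires. The consequence is probably small. The unadjusted loss runs from zero, on the sponsor's assumption, to at most about 11.5% of the effect under linear accrual with every patisiran patient on a Week 6 baseline. At 25% affected, ECV power falls only from 95.2% to 94.0%. An effect that accrues faster than linearly would cost more, but nothing in the documents points to that.

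CMR and scintigraphy are exploratory endpoints (main SAP, Section 3), outside the testing hierarchy of Section 5.7, and any bias is toward no difference, so the rule cannot produce a false claim of benefit. It is a worthwhile, cost-free clarification and does not threaten the trial's conclusions.

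**What to change.** Replace the first sentence of Imaging SAP 5.2 with: *Baseline is the last non-missing value before the first dose of study drug; only if none exists, the earliest non-missing value within 6 weeks after the first dose is used.* Apply the same order of preference to the redefined open-label baseline: the last value from Month 9 onward before the first open-label dose, and only if none exists, the earliest value within 6 weeks after it.

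The cost is two sentences in one document. Every patient who has a baseline now keeps one.

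The change does not affect patients whose only baseline scan is post-dose; any attenuation there remains. To make that visible, report by arm how many patients have a post-dose baseline, and add a sensitivity analysis restricted to pre-dose baselines.
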